### **1. Research Visit 1 – Part 1**

- a. When scheduling this visit, the research team will ensure that the participant and their family are aware of the safety measures at

Children's Mercy Hospital to prevent transmission of the SARS-CoV-2 virus. These resources and information to be shared will be detailed on the Children's Mercy Hospital homepage and any PCRU guidance in response to the COVID-19 pandemic. The research team will discuss with the participant and their family that safety procedures to reduce SARS-CoV-2 transmission will be in place for all in-person visits for the foreseeable future.

- b. Conduct permission/assent with participant and legally authorized representative (LAR), respectively. Obtain a signed and dated, written informed permission/assent form.
  - i. If permission/assent conducted via phone or virtually prior to Research Visit 1 – Part 1, ensure that original copy with participant and LAR is received prior to beginning research procedures.
  - ii. Make a copy of all permission/assent forms for the participant and LAR.
- c. Obtain demographic data: age, gender, race.
- d. Obtain medical history, including prior surgeries.
- e. Obtain history of prior and concomitant medication. Add to Concomitant and Prior Medications Log.
- f. Provide participants and their families the illustrated U54 Study Booklet that will be used to:
  - i. Supplement the information about the study procedures given in the permission/assent form;
  - ii. Record medication administration, and;
  - iii. Detail answers to any questions they have about the study.
  - iv. A questionnaire will be included with the booklet asking families to evaluate how helpful the U54 Study Booklet was in their understanding of the research study. The participant and their parents may also provide feedback for the U54 Study Booklet as well;
  - v. Because this questionnaire and survey are a nested study within the longitudinal study, participants and their families will also be given a handout, (please see supplemental document, "U54 Study Booklet Information Handout,") to explain the purpose of the U54 Study Booklet, the purpose of the questionnaire, and it describes that the responses to the booklet will be anonymous.
  - vi. The U54 Study Booklet Information Handout serves as a permission/assent or consent document and the voluntary return of the questionnaire and survey serves as assumed permission/assent or consent.
- g. Provide handout explaining CHADIS.

- h. Collect information regarding the participant's comfort with needlesticks and ability to swallow pills. Questions include:
  - i. Parent impression about child's anticipated comfort with needlestick
  - ii. History of needlesticks
  - iii. General fears about healthcare settings
  - iv. Fears about unfamiliar situations
  - v. Ability to swallow pills
- i. Collect blood sample for genotyping (~1 mL).
- i. The study team may order topical lidocaine (which for this study refers to either a J-tip or cream) if the study participant requests this for procedures requiring a needlestick.
- j. For enrolled participants where a washout is needed prior to beginning atomoxetine:
  - i. A washout will only be considered for participants currently taking stimulant medication for ADHD. Examples of this include methylphenidate or amphetamine salts.
  - ii. A study physician or qualified study personnel will determine if the washout may be conducted safely. If so, he or she will document approval of the washout on associated CRF. If this conversation occurs via telehealth, the study physician or qualified study personnel may document the conversation electronically and send an approval via email. The CRF and email will be printed and stored in the participant's binder. Persons who are able to approve a washout will be identified in the Delegation of Authority/Roles.
  - iii. Once the washout has been approved, study personnel will review the washout plan with the participant. Study personnel will:
    1. Document any questions or concerns that the participant and family have regarding washout.
    2. Document participant and family's understanding and willingness to complete washout.
    3. Educate families on who to call if issues arise during washout. See "Washout Handout" in Supplementary Documents.
    4. Educate families to restart on medications (particularly if participant was on stimulants) if behaviors while off medication could cause risk to the participant.
  - iv. A 1-week washout period of at least one week is sufficient for children taking stimulants.
  - v. If the child is unable to washout of medication or the study physician does not approve the washout's safety, they will be removed from the study.

- vi. Schedule Research Visit 1 – Part 2 after washout period is anticipated to be completed.
- k. If it is determined that the participant was previously taking and subsequently discontinued any of the following medications (see below) prior to notification of study opportunity, an appropriate time to administer baseline questionnaires and to begin ATX intervention must be determined.
  - i. ADHD medication other than a stimulant, e.g. ATX or  $\alpha_2$ -agonists
  - ii. Selective Serotonin Reuptake Transporter Inhibitor (SSRI)
  - iii. Selective Serotonin/Norepinephrine Reuptake Transporter Inhibitor (SNRI)
  - iv. Any medication that could reasonably be expected to affect neurotransmitter concentrations, such as anxiolytics, antiepileptics, antipsychotics.
  - v. A CYP2D6 inhibitor
  - vi. The following table will be used as guidance for when to administer baseline questionnaires (i.e. return to baseline neurotransmitter levels and/or behavior) and when to begin ATX therapy (i.e. drug and/or active metabolites excreted from participant). However, this only addresses the most common medications that children with ADHD or behavioral concerns are likely to be trialed on.
    - 1. The time indicated in “Medication Washout Interval,” is the minimum amount of time needed for medication to be removed and thus, the amount of time needed before beginning ATX intervention.
    - 2. Administering baseline questionnaires relates to estimating when the participant is likely to return to baseline behavior, which could be longer than the time needed for drug to be removed from systemic circulation. When it is noted that the, “length of pharmacodynamic effects can be variable,” the research team must rely on parent, teacher, and/or participant report of symptoms and function. Evaluation of the participant’s medication chart may be also assessed for this information.
  - vii. A detailed literature search must be conducted for medications not listed here. The process by which this occurs will be described in more detail in Appendix O.

Medication Class/Group	Examples *also CYP2D6 inhibitor (indication)	When to Administer Baseline Questionnaires	Medication Washout Interval (time expected for drug to be removed from systemic circulation)
ADHD Medications (non-stimulants)	atomoxetine	2-4 weeks	CYP2D6 genotype dependent (2- 4 weeks)
	clonidine (sleep)	1-2 weeks	CYP2D6 genotype dependent (1-2 weeks)
	clonidine (ADHD)	2-4 weeks	CYP2D6 genotype dependent (2-4 weeks)
	guanfacine (sleep)	1-2 weeks	May be CYP2D6 genotype dependent (1-2 weeks)
	guanfacine (ADHD)	2-4 weeks	May be CYP2D6 genotype dependent (2-4 weeks)
SSRIs	fluoxetine*	Length of PD effects can be variable	2 months, (inhibits 2D6, 3A4, 2C19)
	sertraline*	Length of PD effects can be variable	1 week, weak inhibitor of CYP2D6
SNRIs	bupropion*	Length of PD effects can be variable	2 – 4 weeks (metabolites primary inhibitors)
	venlafaxine*	Length of PD effects can be variable	1 week, weak inhibitor of CYP2D6
Antipsychotics	aripiprazole	Length of PD effects can be variable	CYP2D6 genotype dependent (1-2 months)
	risperidone	Length of PD effects can be variable	CYP2D6 genotype dependent (1 -2 weeks)
Antiepileptics	levetiracetam	Length of PD effects can be variable	1 week
	valproic acid	Length of PD effects can be variable	1 week (2-4 years, t1/2 3.5 – 20 hours)
Anxiolytics	buspirone	Length of PD effects can be variable	1 week
CYP2D6 Inhibitors	imipramine	Length of PD effects can be variable	2 weeks
	nortriptyline	Length of PD effects can be variable	2 weeks (t1/2 14 -51 hours)
	quinidine	immediately after washout	1 week
	propafenone	immediately after washout	2 weeks
	cimetidine	immediately after washout	1 week (weak inhibitor of CYP2D6)
	tamoxifen	immediately after washout	2 months (may inhibit through competition at active site)
	terbinafine	immediately after washout	6 months
	cetirizine	most likely immediately after washout, however histamine can affect neurotransmitter profile	1 week
	loratadine	most likely immediately after washout, however histamine can affect neurotransmitter profile	1 week

**2. Research Visit 1 – Part 2**

- a. If Research Visit 1 – Part 1 and Research Visit 1 – Part 2 are scheduled on different dates, the research team will ensure that the participant and their family are aware of the safety measures at Children's Mercy Hospital to prevent transmission of the SARS-CoV-2 virus. These resources and information to be shared will be detailed on the Children's Mercy Hospital homepage and any PCRU guidance in response to COVID-19.
- b. For participants where washout was needed: ensure that medication washout (with or without taper) has been completed. Ask about any changes to medical history, including if surgeries occurred between Research Visit 1 – Part 1 and this visit. Add this data to the CRF for Research Visit 1. Ask about any changes to history of prior and concomitant medication. Add to Concomitant and Prior Medications Log.
- c. Measure vital signs: height, weight, blood pressure, heart rate, respiration rate, and temperature.
- d. Perform physical exam.
- e. Perform Tanner Staging. This procedure is optional according to participant preference.
- f. Obtain electrocardiogram reading. Send to cardiologist for interpretation. Sign off that participant has no underlying cardiac disease.
- g. Collect blood samples for safety laboratory tests (processed immediately at Children's Mercy Hospital): CBC with differential, basic metabolic panel, and liver function test.
  - i. The study team may order topical lidocaine (either J-tip or cream) if the study participant requests this for procedures requiring a needlestick.
- h. Collect blood samples for global neurotransmitter metabolomics analysis (pharmacodynamic sample) (2 mL).
- i. Perform urinary pregnancy test for female subjects age 10 and above.
- j. Collect urinary sample for safety laboratory tests (processed immediately at Children's Mercy Hospital): urinalysis with microbiology.
- k. Collect urinary sample for CYP2D6 biomarker measurement (~10 mL).
- l. Collect baseline saliva for microbiome analysis (~2 mL).
- m. Perform assessment of attention tasks (Pupillometry during Posner's Cuing Task). Further details can be found in Appendix H.
- n. Perform psychometric measures to confirm ADHD diagnosis and possible comorbidities:
  - i. Kiddie Schedule for Affective Disorders and Schizophrenia (KSADS) (either paper or K-SADS-COMP). The following sections from the screen interview will be used: agoraphobia, separation anxiety disorder, social anxiety disorder/selective mutism, specific

phobias, generalized anxiety, obsessive compulsive disorder, and post-traumatic stress disorder. Supplemental sections will be filled for the above selected psychopathology as needed (parent and participant informant).

- ii. Kaufman Brief Intelligence Test (KBIT) (participant informant).
    - iii. Behavior Rating Inventory of Executive Function (BRIEF) (parent informant. Teacher informant is optional).
    - iv. Screen for Child Anxiety Related Disorders (SCARED) (parent and if participant  $\geq$  8 years of age)
    - v. Barkley's Sluggish Cognitive Tempo (SCT) (parent informant)
  - o. Administer the following questionnaires:
    - i. Medication Side Effects (parent and teacher informant)
    - ii. NICHQ Vanderbilt Assessment Scale – Initial Assessment (parent and teacher informant)
    - iii. Strengths and Difficulties Questionnaire (parent and teacher informant)
    - iv. Child Behavior Checklist (parent and teacher informant)
    - v. School Intervention Questionnaire (teacher informant)
    - vi. Child Medical History§ (parent informant)
    - vii. Of note, if these questionnaires were obtained within one year of this visit date AND were completed while the participant was not taking ADHD medication, these do not need to be readministered. Additionally, these are clinically validated questionnaires for ADHD. Different versions of these questionnaires are permissible to use to aid the Stuey Physician in a determination a diagnosis.
  - p. Record adverse events. Document in Adverse Events log.
  - q. Create Greenphire account.
  - r. Add compensation to participant's Greenphire account.
  - s. Update Prior Medical History from data collected on questionnaire marked with § above.

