## 4.0 Study Endpoints and Rationale

### 4.1 Primary Study Endpoints

The primary aims of this study focus on characterizing the relationship between changes in pharmacodynamic markers and clinical outcome measures, when inter-subject variability in ATX pharmacokinetics has been minimized (Fig. 3). ATX pharmacodynamics will be measured using plasma DHPG and metabolomic data, pupillometry during attention tasks, and changes in blood pressure and heart rate. Clinical outcomes will be assessed by standardized ADHD measures used in a clinical setting, of which include: NICHQ Vanderbilt Assessment Scale (ADHD symptom rating scale); Strengths and Difficulties Questionnaire; Child Behavior Checklist; the School Intervention Questionnaire; Medication Side Effects; and Clinical Global Impression. Some of these questionnaires will also capture comorbidity information, such as Oppositional Defiant Disorder (ODD). We will also use the Kiddie Schedule for Affective Disorders and Schizophrenia for School-Age Children – Present and Lifetime Version (K-SADS-PL) or K-SADS-COMP (the computerized version of the K-SADS-PL) to diagnose ADHD and commonly associated comorbidities. The K-SADS-PL is a semi-structured interview that is extensively used in clinical psychology research to diagnose an extensive array of psychopathology based on the DSM-5. Given the length of this interview, common research practices are to select only the modules that are expected to be pertinent to the study participant (Black et al., 2012; Kariuki et al., 2018; Caudle et al., 2020). The K-SADS-PL modules selected for this research study are as follows: agoraphobia, separation anxiety disorder, social anxiety disorder/selective mutism, specific phobias, generalized anxiety, obsessive compulsive disorder, and post-traumatic stress disorder. The other research comorbidities or impairments that we will assess for and associated psychometric tests we will use are as follows: impairment in executive function using the Behavior Rating Inventory of Executive Function (BRIEF); anxiety using the Screen for Child Anxiety and Related Disorders (SCARED); intelligence quotient using the Kaufman Brief IQ Test (KBIT); and sluggish cognitive tempo using the Barkley Sluggish Cognitive Tempo Scale (SCT). Pharmacodynamic data will be obtained: baseline (Research Visit 1); when ATX is first initiated in a participant with the first dose (Research Visit 2); when the participant has taken the medication chronically and thus, expected to be at steady-state (Research Visit 3); and at the end of study when the dose has been optimized for the participant (Research Visit 4). Concurrent pharmacokinetic analysis will take place to ensure that ATX plasma and urine exposure variability has been minimized using methods described in a previous ATX pharmacokinetic study conducted at Children's Mercy Hospital (Brown et al., 2016). Additionally, we will measure ATX and metabolites in sweat as surrogate for fraction of drug unbound (Marchei et al., 2012; Marchei et al., 2013). The clinical ADHD questionnaires will be administered at the Intake Visit and at follow-up visits following initiation of atomoxetine treatment (6-weeks, 12-weeks, and

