**9.2 Chart Review**

The following prescreening information will be identified from chart review when possible for Tracks 1-5:

- 6-18 years of age
- Diagnosis or indication of intellectual disability (IQ <70)
- Diagnosis or indication of Autism Spectrum Disorder (ASD)
- Diagnosis or indication of underlying risk for cardiotoxicity, such as presentation of structural cardiac abnormalities, cardiomyopathy, or arrhythmias
- Diagnosis or indication of disease that may cause abnormal absorption or gastric emptying
- Previous history or indication of prior adverse drug reaction to ATX
- Current or previous therapy with drugs used to treat ADHD
- Concurrent or previous therapy with drugs known to inhibit CYP2D6
- Concurrent therapy with other psychiatric/behavioral drugs
- Presence of any of the following questionnaires:
  - Child Medical History
  - NICHQ Vanderbilt Assessment Scale Initial Assessment
  - Child Behavior Checklist
  - Strengths and Difficulties Questionnaire
  - School Intervention Questionnaire
  - Please note: any version of the above questionnaires are permissible for chart review, screening, and recruitment given that these only inform the research team of the *likeness* of participant suitability for the study.

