Research Visit 1 Part 2 takes place in the PCRU and includes obtaining baseline research psychometric measures and baseline safety and research measures to assess for inclusion/exclusion criteria. Psychometric measures will be administered via paper questionnaires, electronically (as with K-SADS-COMP), or obtained using the Comprehensive Health and Decision Information System (CHADIS). K-SADS-COMP was

developed using Microsoft ASP.NET 4.0 framework and Microsoft SQL Server 2016 database. These platforms are stable, reliable and secure. CHADIS is a secure web-based patient questionnaire tool to assist healthcare professionals with their patient clinical care decisions. Parents and caregivers of the study participant are able to complete certain questionnaires online. These results are then imported into the participant's electronic medical record.

The Intake Visit with Study Physician takes place in the Developmental and Behavioral Health Sciences Clinic at the Adele Hall campus, the ADHD Clinic on College Boulevard, or via telehealth. During this visit, the participant and family undergo a routine standard of care visit with a study physician to confirm/infer a diagnosis of ADHD, determine an ADHD subtype, assess for co-morbidities, perform a physical exam, and determine if ATX is an appropriate therapy for the participant. If the Intake Visit occurs via telehealth, all in-person procedures may be omitted. Further details are described in section 11.2. The results from questionnaires will be reviewed. For participants without a formal diagnosis (i.e. documented on participant's electronic medical record), questionnaires must be received from both parent and teacher.

If the subject was seen by a study physician within 6 weeks prior to enrollment and at baseline (meaning not taking any ADHD medication), the visit does not need to be repeated in its entirety. The study physician may amend his or her visit note in the EMR to document the following for research purposes:

- a. Confirm/infer ADHD diagnosis
- b. Assess and confirm/infer diagnosis of other comorbidities
- c. Assess and confirm appropriateness of atomoxetine therapy for participant
- d. Complete Clinical Global Impression (CGI).

After this, the Principle Investigator(s) (PI) will review information from these visits to determine if the participant meets all eligibility criteria.

4. *Intervention assignment*

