#### Pupillometry Analysis:

Changes in performance during Posner Cuing Task will be measured as a function ATX exposure and  $C_{max}$  concentrations. Pupil size will be measured during two types of activities: localization and discrimination tasks. Pupil size differences during localization tasks report on the individuals' baseline (tonic) release of norepinephrine. This corresponds to endogenous, or volitional attention. Pupil size differences during discrimination tasks is a composite of the individuals' baseline (tonic) and situational (phasic) release of norepinephrine. Currently it is unclear whether tonic, phasic, or both are impaired in individuals with ADHD.

Cardiovascular Marker Analysis:

Changes in heart rate will also be measured as a function ATX exposure and  $C_{max}$  concentrations. One side effect of ATX that is directly related to the pharmacodynamics of the drug is an increased heart rate due to increased concentration of norepinephrine in blood. We would like to understand the extent of this side effect as a function of increased systemic ATX exposure and  $C_{max}$ . By studying these two components, we will be able to distinguish ATX drug action in central and peripheral nervous systems.

Pharmacodynamic Changes Correlated with change in NICHQ Vanderbilt Assessment Scales:

All changes markers of pharmacodynamic action will be correlated with whether a child is classified as a responder or non-responder; and tolerant or intolerant (see Clinical Outcomes below for details). Extent of adherence will be used as a confounding factor in both of these analyses.

Clinical Outcomes:

Determine and document participant response to ATX therapy:

- Responders will be defined as:
  - Participants, who after approximately 18 weeks of continuous treatment with ATX, demonstrate  $\geq 40\%$  reduction of baseline ADHD symptom score;
  - OR the Clinical Global Improvement rating is 1 or 2 (Very Much Improved or Much Improved).
- Non-responders will be defined as:
  - Participants, who after approximately 18 weeks of continuous treatment with ATX, demonstrate  $< 40\%$  reduction of baseline ADHD symptom score, AND the Clinical Global Improvement score  $\geq 3$ .
  - Participants who discontinue ATX prior to the planned end of study (18 weeks) due to perceived lack of efficacy despite dose escalation.

Determine and document participant tolerance of ATX therapy:

- ATX intolerant participants are:

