  - Participants who present with side-effects that significantly interfere with daily functioning or outweigh therapeutic benefit (CGI Efficacy Scale categorization)
  - Participants who must discontinue ATX for any of the following reasons: AST or ALT three times the upper limit of normal (ULN) for age, alkaline phosphatase five times the ULN, total bilirubin two times ULN, QT prolongation or dysrhythmia, hypertension (systolic or diastolic BP above 95% for age), tachycardia (HR above 95% for age)

Parent and teacher responses for the NICHQ Vanderbilt Assessment Scales will be obtained at baseline and  $\pm$  2 weeks of 6-week Visit with Study Physician, 12-week Visit with Study Physician, and 18-week Visit with Study Physician. If questionnaires are returned outside of this window, or are unreturned, these will be considered, "missing data." Determination of response, i.e. responder vs. non-responder, will be done using parent responses to questionnaires. Teacher response to questionnaires will also be analyzed to evaluate symptom reduction in a secondary setting. Partial return of teacher questionnaires are still useful in that these data may be used to correct for bias in parental response.

Questionnaires conducted at baseline and at either 18-week visit with Study Physician or a Research Visit will be analyzed for change pre- and post-intervention. These include: BRIEF – parent, SCT, SCARED, CBCL, and School Intervention Questionnaire.

Statistical analyses of clinical response in the population studied will be performed by The Division of Health Services and Outcomes Research at the Children's Mercy Hospital, Kansas City, MO. SAS version 9.4 (SAS, Cary, NC, USA) and R (The R Foundation) will be used to determine if ATX responders and non-responders can be differentiated by a subset of patient specific covariates.

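### A questionnaire up to a year old can serve as the baseline for the 40% responder rule, so off-drug change before treatment is scored as response to atomoxetine

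*Combined protocol and SAP*

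**What the plan says.** Section 4.1 gives the general timing: "The clinical ADHD questionnaires will be administered at the Intake Visit and at follow-up visits following initiation of atomoxetine treatment". Section 20.1 (Clinical Outcomes) says "Parent and teacher responses for the NICHQ Vanderbilt Assessment Scales will be obtained at baseline" and sets a window of two weeks either side for the follow-up forms, but no date or window for the baseline form. Footnote 5 of the Schedule of Events sets only a latest time, the Intake Visit.

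Section 11.2 lists the Vanderbilt, CBCL and School Intervention Questionnaire at Research Visit 1 – Part 2. It then drops the need for a new form "if these questionnaires were obtained within one year of this visit date AND were completed while the participant was not taking ADHD medication".

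Section 20.1 defines a responder at about 18 weeks by at least a 40% "reduction of baseline ADHD symptom score", "OR the Clinical Global Improvement rating is 1 or 2". A non-responder at 18 weeks needs both a smaller reduction and a rating of 3 or more. On the informant it says: "Determination of response, i.e. responder vs. non-responder, will be done using parent responses to questionnaires". It also plans pre/post analyses of the CBCL and School Intervention Questionnaire. It does not name the form that supplies the baseline score, and neither section 20.1 nor 20.2 plans a sensitivity analysis on its age or source.

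**The concern.** The waiver sits beside text about helping the physician reach a diagnosis, and an older off-medication form may serve that purpose well. Measuring change is a different purpose. The study is open-label with no control arm, so nothing separates what happened between the old form and the first dose from what happened on drug. A child who improved off drug in that interval is credited with response, and a child who worsened is charged with non-response.

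Responder status is the outcome for Hypothesis 2 and for the response part of Hypothesis 3, and it forms the groups compared in section 20.2. The baseline neurotransmitter sample, pupillometry, BRIEF, SCARED and SCT carry no such waiver at the same visit. A reused Vanderbilt can therefore be up to a year out of step with the markers it is set against.

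Reuse is foreseeable. Section 9.2 has staff check charts for "Presence of any of the following questionnaires", and the list includes the Vanderbilt. Section 9.3 describes these forms as routine intake at the College Boulevard ADHD clinic, which is actively recruited as Track 1. Section 6.1 admits children who are medication-naïve or currently untreated.

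**Working it through.** **Inputs.** From section 20.1: the 40% threshold, parent-rated, and the alternative CGI route. From section 11.2: the limit of one year before Research Visit 1 – Part 2 and the off-medication condition. The documents give no figure for how many forms are reused or how scores move off drug. Drifts of 10% and 20% in either direction are therefore assumptions chosen to show the mechanism.

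**Step 1: which form is the baseline.** If the waiver is used and no new form is taken, the old form is the only pre-treatment Vanderbilt. It is the baseline by elimination, although section 20.1 does not say so. If two forms exist, nothing says which one counts.

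**Step 2: effect on the threshold.** Let O be the score on the reused form, P the off-drug score just before the first dose, and E the score at 18 weeks. Let x = (O − P)/O, so that x is positive for a fall before treatment and negative for a rise. The rule applied to the old form is met when E ≤ 0.6 × O. Measured from P = (1 − x) × O, the reduction that just meets it is

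1 − E/P = 1 − 0.6/(1 − x).

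- x = 0 (no drift): 1 − 0.6/1.0 = 40.0%, the plan's own threshold
- x = 0.10: 1 − 0.6/0.9 = 33.3%
- x = 0.20: 1 − 0.6/0.8 = 25.0%
- x = −0.10: 1 − 0.6/1.1 = 45.5%
- x = −0.20: 1 − 0.6/1.2 = 50.0%

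After a 10% prior fall, a child whose score drops on drug by between 33.3% and 40% is called a responder on the symptom route. After a 10% prior rise, a child whose score drops by between 40% and 45.5% fails it.

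**Step 3: the CGI route.** The two routes are joined by OR. A child rated 1 or 2 is a responder whatever the Vanderbilt baseline, so the rating can rescue a false non-responder. A child who passes the 40% route falsely stays a responder even with a rating of 3 or more. The protection therefore runs one way.

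**Step 4: who is exposed.** A child on a stimulant throughout the previous year has no older off-medication form to reuse. Track 4 families are sent the study forms after consent. For Track 5, section 9.3 takes baseline results from forms completed before the Summer Treatment Program and does not say whether they replace the form at Research Visit 1 – Part 2.

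**The case against.** A reader might infer that the waiver contradicts sections 4.1 and 20.1. It does not. Neither section sets an earliest date, and a form completed earlier satisfies the Schedule's requirement of completion by the Intake Visit. The waiver is an open allowance.

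Nor is the age of the form unlimited, because section 11.2 caps it at one year before Research Visit 1 – Part 2. The protocol also treats baseline largely as an off-medication state: section 11.1 glosses it that way, and the washout table and Appendix O tie baseline questionnaires to return to baseline behavior. The waiver's off-medication condition fits that idea. What stands is that being off medication does not make a score current.

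Section 11.1 lets an earlier physician visit stand in only under a tighter limit ("If the subject was seen by a study physician within 6 weeks prior to enrollment and at baseline"). That concerns a clinical visit and is not a standard for the age of a rating scale, so little weight rests on it.

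Forms on file may also be only weeks old, since recruitment in Tracks 1 and 2 is built around clinic appointments. That is possible, but the plan records nothing that would show it. Finally, a new form at Research Visit 1 – Part 2 does not remove all drift, because the Schedule sets no windows for Research Visit 1, Intake or Research Visit 2. That is a reason to record the interval to first dose.

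**Conclusion.** The point holds as a design weakness that should be corrected. Followed as written, the plan lets off-drug change over a period that can reach a year enter the responder classification, and the same applies to the CBCL and School Intervention change scores. The shift in effective threshold in step 2 is exact for a given drift; the drift values are assumed.

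A reader might go further and infer a particular number of misclassified children or a loss of power for the comparisons in section 20.2. The documents do not support either. Both depend on the reuse share, the drift and the number of children whose status turns on the 40% route alone, and none of these is given. Only children with a reused form can be affected, and children rated 1 or 2 on the CGI are responders in any case. The effect may be small; the plan as written provides no way to find out.

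**What to change.** - **Section 11.2:** limit the waiver to diagnosis and eligibility. Collect the already listed parent Vanderbilt, off medication, at Research Visit 1 – Part 2 from every remaining participant.
- **Section 20.1:** name the last off-medication parent Vanderbilt before the first dose as the baseline for the 40% rule.
- **Data:** record the completion date of every baseline form, including those already reused.
- **Analysis:** add a sensitivity analysis that excludes children with reused forms or adjusts for time from form to first dose. Do the same for the CBCL and School Intervention change scores.
- **Track 5:** reconcile section 9.3 with section 11.2 on whether forms completed before the Summer Treatment Program may replace the study form.

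The cost is one short extra parent form for some families, an amendment and a small added analysis. Section 10.1 expects procedures to end by June 2022, so new collection may reach few children. For data already collected, the form dates, the baseline definition and the sensitivity analysis are the main remedy.
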